**PROTOCOL CA209032**

**VERSION # 2.0**

**TABLE 1: REVISION HISTORY**

Revision	Date	Revised By	Changes Made -- Reasons for the Change
1.0	07 OCT 2013		Original issue
2.0	26 FEB 2016		
Incorporates Amendments 08, 09, and 10.
 
Summary of changes:
 
Amendment 08 is to add nivolumab 3 mg/kg in combination with ipilimumab 1 mg/kg to the dose levels being investigated in study CA209-032, change the bladder cohort to a One Stage Design.
 
Amendment 09 includes:
 
 
• SCLC and Bladder: arms Nivo 3 mg/kg and Nivo 1/ Ipi 3 mg/kg, increase sample size.
 
• Updates to Blinded Independent Central Review (BICR) information
 
• Updates to Primary, Secondary [REDACTED] Objectives
 
 
Amendment 10 includes:
 
 
• Regimen NI2c was added for treatment of ovarian cancer.
 
• For subjects from NI combination who undergo a re-exposure if they achieved an initial objective response (PR or CR) or stable disease of > 3 months and had a subsequent documented progression, an option to continue treatment with nivolumab monotherapy if ipilimumab treatment was stopped due to toxicity is added. (see Section 2.4 for details)
 

## **2 STUDY DESCRIPTION**

### **2.1 Study Design**

This is a Phase 1/2, open-label study of nivolumab monotherapy (Arm N), or nivolumab combined with ipilimumab (Arm N-I) in adult ( $\geq 18$  years) subjects with advanced or metastatic cancer of the following types:

- 1) Triple Negative Breast Cancer (TNBC)
- 2) Gastric or Gastro-Esophageal Junction Carcinoma (GC)
- 3) Pancreatic Cancer (PC)
- 4) Small Cell Lung Cancer (SCLC)
- 5) Bladder Cancer (BC).
- 6) Ovarian Cancer (OC)

The assignment to treatment arm and evaluation of safety and activity will be performed independently for each tumor type. For each tumor type, subjects will be assigned to one of these treatment arms:

**Arm N:** Nivolumab monotherapy (3 mg/kg) Q2W

**Arm N-I Dose Level 1:** Nivolumab (1 mg/kg) + Ipilimumab (1 mg/kg) Q3W for 4 doses, then Nivolumab (3 mg/kg) Q2W

**Arm N-I Dose Level 2:** Nivolumab (1 mg/kg) + Ipilimumab (3 mg/kg) Q3W for 4 doses, then Nivolumab (3 mg/kg) Q2W

**Arm N-I Dose Level 2b:** Nivolumab (3 mg/kg) + Ipilimumab (1 mg/kg) Q3W for 4 doses, then Nivolumab (3 mg/kg) Q2W

**Arm N-I Dose Level 2c:** Nivolumab (3 mg/kg) Q2W + Ipilimumab (1 mg/kg) Q6W

Additional cancer types may also be added in the future. The addition of any new cancer types will not affect the statistical analysis plan. All analyses related to the additional cancer types will be performed exactly as described in this SAP.

**Dose-Escalation Safety Evaluation Phase for Combination Arm:** Although the regimen currently used in the phase 3 melanoma study, nivolumab 1 mg/kg IV + ipilimumab 3 mg/kg, was expected to also be tolerable in the tumors studied here, an initial dose-escalating safety evaluation for the combination arms was conducted for each subject with GC, PC, TNBC, or SCLC. The BC cohort was added to this protocol following the completion of the safety evaluations in GC, PC, TNBC, and SCLC at dose level 1 (nivolumab 1 mg/kg, ipilimumab 1 mg/kg) which did not reveal safety concerns. Thereby the starting dose level for the BC cohort was dose level 2 (nivolumab 1 mg/kg, ipilimumab 3 mg/kg). Six BC patients were initially randomized to Dose Level 2, after which enrollment to Dose Level 2b (nivolumab 3 mg/kg, ipilimumab 1 mg/kg) began.

Enrollment to Stage 1 for Arm N will occur in parallel to the safety evaluation for Arm N-I.

**Modified Design for Bladder Cancer Cohort:**

Bladder arms N and N-I (Dose Levels 2 and 2b) will be conducted as a One Stage Design with the treatment of 26-105 subjects in each arm. The Safety Evaluation Phase for the N-I arm will start at Dose Level 2 (nivolumab 1 mg/kg, ipilimumab 3 mg/kg) and will evaluate safety and tolerability after the first 6 randomized subjects. Following the N-I safety evaluation phase, Dose Levels 2 will enroll 26 subjects and 2b will enroll up to a total of 105 subjects. Based on the safety evaluations thus far on study, no dose escalation phase is necessary for bladder cohort N-I Dose Level 2b (nivolumab 3 mg/kg, ipilimumab 1 mg/kg).

**Modified Design for Ovarian Cancer Cohort:**

Ovarian arm N-I (Dose Levels 2, 2b and 2c) will be conducted as a One Stage Design with the treatment of 40 subjects in each arm. Based on the safety evaluations thus far on study, no dose escalation phase is necessary for ovarian cohort N-I Dose Levels.

**SCLC Expansion:**

SCLC cohorts Arm N and Arm N-I met the pre-specified safety and efficacy criteria and proceeded to Stage 2. Based on an interim data review, disease control rates (SD + PR + CR) of 36% and 57% for Arms N and N-I, respectively, were estimated. In order to further investigate nivolumab and nivolumab combined with ipilimumab activity in specific SCLC subpopulations, the SCLC expansion cohorts will enroll additional subjects based on response to prior treatment and the number of previous therapies. Up to 250 second or third line subjects will be randomized in a 3:2 ratio to one of 2 expansion groups: Arm A (75 second line subjects and 75 third line subjects treated with nivolumab 3 mg/kg every 2 weeks (Q2W)) or Arm B (50 second line subjects and 50 third line subjects treated with nivolumab 1 mg/kg + ipilimumab 3 mg/kg every 3 weeks (Q3W) for 4 cycles followed by nivolumab 3 mg/kg Q2W) and will be stratified for number of prior treatment lines (1 vs 2 prior chemotherapy regimens). Each arm will be limited

to 50% second line and 50% third line subjects to allow a meaningful subgroup evaluation for subjects with second-line versus third-line disease.

**Two Stage Design:** GC, PC, TNBC, or SCLC Arms N and N-I will follow a two-stage design to test whether nivolumab monotherapy or nivolumab combined with ipilimumab yields an objective response rate (ORR) that is of clinical interest in the investigated tumor types. For each tumor type, only treatment arms which meet an ORR threshold will proceed from Stage 1 to Stage 2 (described in protocol Section 3.2.2). Enrollment to Stage 2 in a given treatment arm can continue even if the other treatment arm is still in Stage 1. For TNBC and PC, the assessment of Dose Level 2b (nivolumab 3 mg/kg, ipilimumab 1 mg/kg) was assessed independently as a 2 Stage Design, regardless of efficacy results in the other dose cohorts.

For Stage 2, additional subjects will be assigned into Arm N, and Arm N-I up to a total of 100 subjects (including those assigned in Stage 1) in each treatment arm of the given tumor type. For tumor types where nivolumab monotherapy or nivolumab 1 mg/kg plus ipilimumab 3 mg/kg proceeded to Stage 2, assessment of Dose Level 2b in Stage 2 (nivolumab 3 mg/kg + ipilimumab 1 mg/kg, n= up to 60 subjects) will be initiated for that tumor type. For SCLC, an additional 150 2L and 3L subjects (50% each) will be added in the nivolumab monotherapy arm, 100 2L and 3L subjects (50% each) will be added to N-I dose level 2.

**Crossover for subjects in Arm N:** Subjects in Arm N may crossover to Arm N-I if all of the following criteria are met:

- The Safety Evaluation Phase for the N-I regimen has been completed and at least 6 subjects have been exposed to the dose level used for Stage 1 of the N-I regimen. In case Dose Level 2b has been activated and completed the safety assessment, subjects for cross over will be assigned to Dose Level 2b.
- Subject has confirmed radiologic disease progression (investigator-assessed RECIST 1.1-defined progression confirmed at least 4 weeks after the initial tumor assessment showing progression) in the absence of clinical deterioration. For subjects with clear evidence of new or progressing brain metastases a confirmation is not required. These subjects may proceed with brain radiation therapy and after having completed the radiation therapy a cross over to Arm N-I can be considered
- Subject has not experienced nivolumab related adverse events leading to permanent discontinuation.
- Subject is not continuing to derive any clinical benefit from nivolumab single agent therapy as assessed by the investigator which would allow continuation of nivolumab monotherapy.
- The individual case must be discussed with the medical monitor prior to cross over.

Subjects crossing over to Arm N-I will start treatment at Day 1 Week 1 as described for subjects originally assigned to Arm N-I. Subjects who cross over and subsequently have an objective response in Arm N-I will not be considered in the decision making for Arm N-I proceeding to Stage 2.

## 2.2 Treatment Assignment

The subject number will be assigned through an interactive voice response system (IVRS) once the subject has signed the informed consent form and is registered. Every subject that signs the informed consent form must be assigned a subject number in IVRS. Specific instructions for using IVRS will be provided to the investigational site in a separate document.

The investigator or designee will register the subject for enrollment by following the enrollment procedures established by BMS. The following information is required for enrollment:

- Date that informed consent was obtained
- Date of birth
- Gender at birth

Once enrolled in IVRS, enrolled subjects that have met all eligibility criteria will be ready for treatment assignment and drug vial assignment through the IVRS. The following information is required for drug vial assignment and randomization:

- Subject number
- Date of birth
- Tumor Type
- Date tumor tissue sample was shipped to central lab

Subjects meeting all eligibility criteria will be assigned to Arm N (nivolumab), or Arm N-I Dose Level 2 (nivolumab 1 mg/kg + ipilimumab 3 mg/kg) or Arm N-I Dose Level 2b (nivolumab 3 mg/kg + ipilimumab 1 mg/kg) or Arm N-I Dose Level 2c (nivolumab 3 mg/kg every 2 weeks + ipilimumab 1 mg/kg every 6 weeks) according to their tumor type and treatment arm availability:

- Within a given tumor type, subjects will be assigned to a treatment arm (N, or N-I Dose Level 2 or N-I Dose Level 2b) in a 1:1:1 ratio guided by randomization schedule if all arms are open.
- The computer-generated randomization schemas will be prepared by a Randomization Coordinator within the Drug Supply Management Department of BMS Research and Development.
- If only one or two treatment arms are open for enrollment (ie., when enrollment in Arm N-I is paused for an interim safety assessment, or when either arm is paused for decision making to proceed from Stage 1 to Stage 2 in the Efficacy Signal Detection part), then all newly to be assigned subjects will go into the remaining open arms.
- Once the subject has a treatment assignment, study treatment should be initiated within 3 working days.
- Specific instructions (including an enrollment worksheet) for central enrollment and treatment assignment procedure will be provided to the site.

Subjects to be enrolled in the SCLC expansion cohort will be randomized in a 3:2 ratio to one of 2 expansion groups: Arm A (150 subjects, nivolumab 3 mg/kg every 2 weeks (Q2W) or Arm B (100 subjects, nivolumab 1 mg/kg + ipilimumab 3 mg/kg every 3 weeks (Q3W) for 4 cycles

followed by nivolumab 3 mg/kg Q2W) and will be stratified for number of prior treatment lines (1 vs 2 prior chemotherapy regimens).

Subjects to be enrolled in the OC expansion cohort will be randomized in a 1:1:1 ratio to one of 3 dose level groups:

- Arm A (40 subjects, nivolumab 1 mg/kg + ipilimumab 3 mg/kg every 3 weeks (Q3W) for 4 cycles followed by nivolumab 3 mg/kg Q2W)
- Arm B (40 subjects, nivolumab 3 mg/kg + ipilimumab 1 mg/kg every 3 weeks (Q3W) for 4 cycles followed by nivolumab 3 mg/kg Q2W)
- Arm C (40 subjects, Nivolumab (3 mg/kg) Q2W + ipilimumab (1 mg/kg) Q6W)

### **2.3 Blinding and Unblinding**

Not applicable. This is an open-label study.

### **2.4 Protocol Amendments**

Amendments 1 - 5 did not affect the statistical analysis. Amendment 07 is to update pharmacogenetics blood sample to include all current and future tumor types. Amendment 08 is to add nivolumab 3 mg/kg in combination with ipilimumab 1 mg/kg to the dose levels being investigated in study CA209-032, change the bladder cohort to a One Stage Design, and to add an optional external evaluation of CT or MRI scans for tumor types where data from study CA209-032 will potentially be used for future NDA submissions. Other changes were made to resolve minor inconsistencies and clarifications.

Amendment 09 includes:

- SCLC and Bladder: arms Nivo 3 mg/kg and Nivo 1/ Ipi 3 mg/kg, increase sample size.
- Updates to Blinded Independent Central Review (BICR) information
- Allowing brain radiation prior to cross over
- Allowing retreatment upon PD for patients with long lasting PR or CR and who had treatment held by investigator
- For the combination arm, subjects who meet discontinuation criteria will be allowed to continue with nivolumab treatment should the study related toxicities be attributed to ipilimumab. Ipilimumab would be discontinued.
- Updates to Primary, Secondary ██████████ Objectives
- Updates to Discontinuation criteria to include Grade 4 lymphocytopenia
- Updates to EQ-5D collection

Amendment 10 includes:

- Clarification regarding PK/immunogenicity sampling and pregnancy test was added.

- To characterize the immunogenicity of nivolumab monotherapy, or nivolumab and ipilimumab when combined.
- To evaluate the pharmacodynamic activity of nivolumab monotherapy, or nivolumab combined with ipilimumab in the peripheral blood and tumor tissue as measured by flow cytometry, immunohistochemistry, soluble factor analysis, and gene expression (microarray technology, quantitative RT-PCR).

• [REDACTED]

[REDACTED]

## **4 ENDPOINTS**

### **4.1 Primary**

#### **4.1.1 Objective Response Rate**

The primary endpoint is the objective response rate (ORR). The ORR is defined as the number of subjects with a best overall response (BOR) of complete response (CR) or partial response (PR) divided by the number of treated subjects. The BOR is defined as the best response designation, as determined by the investigator, recorded between the date of treatment assignment and the date of objectively documented progression per RECIST 1.1 or the start date of subsequent anti-cancer therapy, whichever occurs first. CR or PR determinations included in the BOR assessment must be confirmed by a second scan no less than 4 weeks after the criteria for response are first met. For subjects without documented progression or subsequent therapy, all available response designations will contribute to the BOR assessment. For subjects who continue treatment beyond progression, the BOR should be determined based on response designations recorded up to the time of the initial RECIST 1.1-defined progression.

These measures of response will be interpreted in the context of historical responses observed following treatment with approved agents.

### **4.2 Secondary**

The secondary objective (to assess the safety and tolerability of nivolumab monotherapy or nivolumab combined with ipilimumab in subjects with advanced or metastatic tumors) will be primarily assessed by the rate of treatment-related AEs leading to drug discontinuations during the first 12 weeks of treatment. In addition, safety and tolerability will be analyzed through the incidence of adverse events, serious adverse events, and specific laboratory abnormalities (worst grade) in each cohort. Toxicities will be graded using the National Cancer Institute (NCI) Common Terminology Criteria for Adverse Events (CTCAE) version 4.0.

ORR will be further characterized by the duration of response (DOR) and the magnitude of reduction in tumor volume. DOR will be computed for subjects with a BOR of PR or CR and is defined as the time from first confirmed response (CR or PR) to the date of the first documented

tumor progression as determined using RECIST 1.1 criteria or death due to any cause, whichever occurs first. For subjects who neither progress nor die, the DOR will be censored on the date of their last evaluable tumor assessment. Subjects who start subsequent therapy without a prior reported progression will be censored at the last evaluable tumor assessments prior to initiation of the subsequent anticancer therapy. The magnitude of reduction in tumor volume is defined as the percent decrease in tumor volume from baseline to nadir, observed up until the time of the first documented tumor progression or death.

Progression free survival (PFS) is defined as the time from first dosing date to the date of the first documented progression, as determined by the investigator or BICR for selected tumor type (per RECIST 1.1), or death due to any cause, whichever occurs first. Subjects who die without a reported progression or start of any subsequent anti-cancer therapy will be considered to have progressed on the date of their death. Subjects who did not progress or die will be considered as not progressed and will be censored on the date of their last evaluable assessment or last evaluable assessment prior to crossover. Subjects who did not have any on study assessments and did not die will be censored on the first dosing date. Subjects who started any subsequent anti-cancer therapy without a prior reported progression will be censored at the last evaluable assessment prior to initiation of the subsequent anti-cancer therapy.

**Table 4.2: Censoring scheme used in primary analysis of PFS**

Situation	Date of Progression or Censoring	Outcome
No baseline tumor assessments and no death	First Dosing date	Not Progressed
No on study tumor assessments and no death	First Dosing date	Not Progressed
Progression documented between scheduled visits	Date of the first documented tumor progression per RECIST 1.1	Progressed
Clinical progression without evidence of progression per RECIST 1.1 or No progression	Date of last tumor assessment with no documented progression or last evaluable assessment prior to crossover (for crossover subject without PD)	Not Progressed
New anticancer treatment started without a prior reported progression	Date of last tumor assessment prior or on the date of initiation of the subsequent anti-cancer therapy	Not Progressed
Death without progression per RECIST 1.1	Date of death	Progressed

OS is defined as the time between the first dosing date and the date of death due to any cause. A subject who has not died will be censored at the last known alive date. OS will be followed continuously while subjects are on the study drug and every 3 months via in-person or phone contact after subjects discontinue the study drug.

## 5 SAMPLE SIZE AND POWER

### Sample size determination in the original protocol

This study comprises of a Dose Escalating Safety Evaluation Phase for the Combination Arm, followed by a Staged Enrollment for Arm N, and Arm N-I.

In the original protocol, gastric cancer, small cell lung cancer, triple negative breast cancer, and pancreatic cancer are included and the Staged Enrollment Part utilizes a modified Simon two-stage design with the treatment of 40 subjects to evaluate whether nivolumab, or the combination of nivolumab/ipilimumab yields an objective response rate (ORR) that is of clinical interest. In this study, an ORR of 10% or less is considered not of clinical value, and an ORR of 25% or greater is considered of strong clinical interest. The modified Simon design evaluates the null hypothesis that the true response rate is  $\leq 10\%$  versus the alternative hypothesis that the true response rate is  $> 10\%$ . The 2-stage testing within each cohort targets a Type I error rate of 5% and has 80% power to reject the null hypothesis if the true response rate is 25%.

### Sample size determination for bladder cancer cohort

In Amendment 06, bladder cohort is added. One stage design with the treatment of 60-100 subjects is used. These sample sizes provide 90% to 97% power to reject the null hypothesis of 10% response rate if the true response rate is 25% with a two-sided Type I error rate of 5%.

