### **7.5.1 Objective Response Rate**

#### **7.5.1.1 Primary Analysis**

ORR will be summarized for each cohort by a binomial response rate and corresponding two-sided 95% exact CI using the method proposed by Atkinson and Brown for cohorts using two-stage design and Clopper and Pearson method for cohorts using one stage design.

DOR will be summarized for subjects who achieve confirmed PR or CR using the Kaplan-Meier product-limit method. Median values of DOR, along with two-sided 95% CI using the log-log transformation will also be calculated by cohort. In addition, the percentage of responders still in response at different time points (3, 6, and 12 months) will be presented based on the KM plot.

For SCLC expansion cohorts, similar methods will be used to summarize ORR and DOR for each stratification factor.

The magnitude of reduction in tumor burden will be summarized descriptively.

For the analyses of crossover subjects during original assigned treatments, ORR data will be truncated prior to the first crossover dose date. For the analysis of crossover subjects during crossover period, ORR will also be summarized. Baseline will be re-established. BOR, PR, and CR will be re-derived starting on the date of crossover.

In addition, percent change from baseline based on the target lesions will be plotted overtime for each subject grouped by treatment arm (spider plot). For crossover subjects, data will be truncated prior to the first date of crossover.

Time on therapy and time to response will also be plotted for each subject with symbols indicating time of radiographic progression, LKDA, first response, last dose, last dose when subject off treatment, crossover, and death (swimmer plot). For crossover subjects, no data will be truncated.

- A plot of individual time course of tumor burden change per investigator assessment but limited to subjects who were treated beyond progression.

Among subjects treated beyond progression, non-conventional benefitters will be identified and will be defined as subjects who had not experienced a BOR of PR/CR prior to initial RECIST-defined progression, and met at least one of the following:

- Criterion 1: Appearance of a new lesion followed by decrease from baseline of at least 10% in the sum of the target lesions.
- Criterion 2: Initial increase from nadir  $\geq 20\%$  in the sum of the target lesions followed by reduction from baseline of at least 30%.

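### Section 5 gives bladder power for 60-100 subjects (90% to 97%), but Section 2.1 plans 26 in Dose Level 2, where power is about 66% (48.5% on the planned Clopper-Pearson interval)

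*SAP*

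**What the plan says.** All references are to the multi-tumour SAP, version 2.0.

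- **Section 5, bladder cohort.** "One stage design with the treatment of 60-100 subjects is used. These sample sizes provide 90% to 97% power", introduced as an Amendment 06 decision. The power is for rejecting a 10% response rate when the true rate is 25%, at a two-sided Type I error of 5%. No arm is named. This is the only power statement for bladder cancer.
- **Section 2.1, modified bladder design.** Arm N and the two combination dose levels "will be conducted as a One Stage Design with the treatment of 26-105 subjects in each arm". After the safety evaluation in six subjects, "Dose Levels 2 will enroll 26 subjects and 2b will enroll up to a total of 105 subjects". Arm N gets no number of its own beyond the 26-105 range.
- **Section 2.4 and the revision history.** Amendment 09 is summarised as "SCLC and Bladder: arms Nivo 3 mg/kg and Nivo 1/ Ipi 3 mg/kg, increase sample size". The second of these regimens is Dose Level 2.
- **Section 7.5.1.1.** The response rate is reported with a two-sided 95% exact interval: "Clopper and Pearson method for cohorts using one stage design".

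**The concern.** Sections 2.1 and 5 are both current text and describe the same one-stage bladder design with different sizes. An arm of 26 is less than half the smallest size that Section 5 covers, and nothing in the SAP gives power or precision for it. A reader who takes the Section 5 range as covering every bladder arm would credit Dose Level 2 with at least a 90% chance of excluding a 10% response rate when the true rate is 25%. Section 5 describes 25% as a rate of strong clinical interest in the original four tumour types, and the bladder power statement uses the same alternative. ORR is the primary endpoint, and Section 7.5.4 says bladder interim results will support internal decisions and publication. The operating characteristics of the smallest arm should therefore be stated correctly.

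**Working it through.** **Inputs.** Null rate p0 = 0.10, alternative p1 = 0.25, two-sided 5%, n = 60 to 100 (Section 5). n = 26 and up to 105 (Section 2.1). Clopper-Pearson 95% interval (Section 7.5.1.1). X is the number of responders, binomial(n, p).

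**Three criteria**

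1. Normal approximation, two-sided, null variance under H0: power = Φ{[(p1 − p0)√n − 1.96√(p0(1 − p0))] / √(p1(1 − p1))} = Φ{[0.15√n − 1.96 × 0.300] / 0.433}.
2. Exact two-sided binomial test at 5% (minimum-likelihood p-value).
3. Clopper-Pearson lower limit above 10%, which is the same as requiring an upper-tail probability under 10% of at most 0.025.

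**Step 1: reproduce the stated 90% to 97%**

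- Normal, n=60: [0.15 × 7.746 − 0.588]/0.433 = 1.325, power 90.7%.
- Normal, n=100: [1.5 − 0.588]/0.433 = 2.106, power 98.2%.
- Exact two-sided: 91.4% at n=60 and 97.9% at n=100.
- Clopper-Pearson: 85.2% at n=60 (at least 12 responders) and 97.9% at n=100 (at least 17).

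Criteria 1 and 2 come within about 1.5 points of the stated figures. Criterion 3 does not give 90% at n=60. The stated range is therefore correct for its own sizes and rests on something like criterion 1 or 2.

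**Step 2: the same criteria at the Section 2.1 sizes**

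| n | Normal, two-sided | Exact two-sided | Clopper-Pearson lower limit > 10% |
|---|---|---|---|
| 26 | 65.9% | 66.3% (at least 6) | 48.5% (at least 7) |
| 60 | 90.7% | 91.4% (at least 11) | 85.2% (at least 12) |
| 100 | 98.2% | 97.9% (at least 17) | 97.9% (at least 17) |
| 105 | 98.6% | 98.9% (at least 17) | 97.9% (at least 18) |

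Detail for n=26:

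- Normal: [0.15 × 5.099 − 0.588]/0.433 = 0.408, and Φ = 65.9%.
- P(X ≥ 6 | 0.10) = 0.0399 and P(X ≥ 6 | 0.25) = 0.6629.
- P(X ≥ 7 | 0.10) = 0.0119 and P(X ≥ 7 | 0.25) = 0.4846.
- 6/26 = 23.1% has a Clopper-Pearson 95% interval of 9.0% to 43.6%, which includes 10%. 7/26 has a lower limit of 11.6%.

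**Step 3: is 26 the total?** Section 2.1 places the enrolment of 26 after the six-subject safety evaluation. If the six are extra, n=32 and power is 56.8% (Clopper-Pearson, at least 8), 72.2% (exact two-sided) or 72.6% (normal). The per-arm range of 26-105 favours 26 as the total, but either reading leaves power well below 90%.

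**Size of the gap.** Against the 90% lower bound, the shortfall at n=26 is about 24 points like for like (90 − 66) and about 42 points on the planned interval (90 − 48.5).

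**The case against.** The strongest reply is that Section 5 contains no arithmetic error. Its power range is tied to 60-100 subjects and reproduces there. It names no arm, whereas the ovarian paragraph gives its size for each arm. That stands: the defect is a failure to align Section 5 with Section 2.1, not a miscalculation.

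Four stronger readings are tempting, and the documents do not support them.

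- **That the true power is simply 48%.** That figure uses a stricter rule than the one behind the stated range: the same rule gives 85.2%, not 90%, at n=60. The like-for-like figure is about 66%. The 48.5% is relevant because it matches the interval that will be reported, but it should be labelled as such.
- **That no arm fits 60-100.** Dose Level 2b is capped at 105, so it could finish inside that range. Arm N has no size of its own to compare. The material conflict is with Dose Level 2.
- **That 26 is the correct number and Section 5 the only error.** The Amendment 09 summary says that the sample size of this regimen's bladder arm was increased, which sits badly with 26 as the final figure. The SAP does not settle which figure is current.
- **That a wrong go/no-go decision would follow.** Section 7 contains no success rule or hypothesis test for bladder. It plans a rate with an exact interval, and Section 4.1.1 says response will be read against historical results. Misreading a non-excluding result as a well-powered negative is a risk, not a planned step.

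Section 5 cannot be set aside as a frozen record of Amendment 06. By the SAP's own account the change to a one-stage bladder design came with Amendment 08, version 2.0 incorporates Amendments 08 to 10, and no later power statement replaces this one.

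**Conclusion.** The point holds as an unreconciled size with a power statement that does not carry over. For a 26-subject bladder arm, 10% against 25% at two-sided 5%, power is about 66% by the methods that reproduce the stated range, and 48.5% if success means a Clopper-Pearson lower limit above 10%. A regimen with a true rate of 25% would therefore fail to exclude 10% about one time in three (100 − 66 = 34%) or about one time in two (100 − 48.5 = 51.5%). Section 5 would suggest at most one in ten.

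This assumes that 26 is the intended total for Dose Level 2. With 32 subjects, power is 57% to 73% and the conclusion is the same. If reconciliation shows a planned size of 60 or more, the stated power is recovered by the two-sided methods, and the error lies in Section 2.1 instead. Dose Level 2b at its cap is not a problem.

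**What to change.** 1. Reconcile the bladder arm sizes across Section 2.1, Section 5 and the Amendment 09 entries in the revision history and Section 2.4. State whether the six safety subjects are included in the Dose Level 2 number.
2. Restate the bladder paragraph of Section 5 per arm, naming one power method and using it throughout.
3. If Dose Level 2 stays at 26, give its power as about 66% (two-sided exact or normal) or 48% (Clopper-Pearson lower limit above 10%, at least 7 responders), whichever method is named. Add the precision, for example 6/26 with a 95% interval of 9.0% to 43.6%.
4. Give Dose Level 2b its figure at 105 (about 98% on the Clopper-Pearson rule), and give Arm N its own size and figure.

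The cost is SAP wording only. Enrolment, endpoint, population and planned interval are unchanged. The one consequence is a less favourable stated power for one arm if 26 is confirmed.
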